8.3. Exclusion Criteria

Eligible patients who meet any of the following criteria during the screening period should be excluded from the study:

1. Current or ongoing exposure to the trauma that resulted in the PTSD.
2. Increased risk of suicide on the basis of the Investigator's judgment and/or the results of the Mini International Neuropsychiatric Interview, Version 7.0.2 (M.I.N.I. 7.0.2) conducted at Screening and the Columbia Suicide Severity Rating Scale (C-SSRS) conducted at Screening and/or Baseline and Item 10 of the Montgomery-Åsberg Depression Rating Scale (MADRS) at Screening and/or Baseline. Any of the following will be exclusionary:
 - a. High suicidality based on a M.I.N.I. Module B score ≥ 17 (Screening); or,
 - b. Patient answers YES to either M.I.N.I. question B10 or B11 (Screening); or,
 - c. Patient meets criteria for CURRENT Suicidal Behavior Disorder on the M.I.N.I (Screening); or,
 - d. C-SSRS Type 4 or Type 5 ideation within 6 months of Screening or at the Baseline visit; or,
 - e. Any suicidal behavior in the past 12 months as identified by the C-SSRS at Screening or Baseline.
 - f. A score of > 4 on Item 10 of the MADRS at Screening or Baseline.
3. Increased risk of suicide, based on the Investigator's judgment that is of a severity that is not appropriate for outpatient management, or that warrants additional therapy excluded by the protocol.
4. Significant (e.g., moderate or severe) comorbid traumatic brain injury (TBI) by history. Based on past history and Investigator's judgment, patients with mild TBI are eligible.
5. Severe depression suggested by a Screening (Visit 1) MADRS score > 26 . Patients with a Screening MADRS score of ≥ 26 may be randomized upon Medical Monitor approval, based on a review of all Screening rating scales and the patient's psychiatric/medical history.
6. Clinically significant laboratory abnormalities based on screening laboratory tests and/or medical history in the Investigator's opinion, including a Thyroid Stimulating Hormone (TSH) level > 1.5 times the upper limit of normal and aspartate aminotransferase (AST) and/or alanine aminotransferase (ALT) > 3 times the upper limit of normal (if persistent upon repeat). Patients with treated thyroid conditions and TSH levels ≤ 1.5 times the upper limit of normal will be eligible to participate in the study.

7. Diagnosed with clinically significant and currently relevant cardiac disease (e.g., significant arrhythmia or heart block, heart failure) or recent myocardial infarction [within the past 2 years] or QTcF > 450 msec (male) or > 470 msec (female) on the screening electrocardiogram (ECG).
8. Current evidence of human immunodeficiency virus (HIV) infection based on screening laboratory results or medical history, or clinically significant hepatitis B or C infection as defined by current treatment or liver function tests (e.g., aspartate aminotransferase [AST] or alanine aminotransferase [ALT] > 3 times the upper limits of normal).
9. Use of antidepressant medication within 2 months of baseline, with the exception of trazodone used at doses \leq 150 mg per day or tricyclic antidepressants at doses \leq 50 mg per day for the purpose of treating insomnia, which instead require a 1-week drug-free interval prior to the Baseline visit.
10. Unable to successfully wash out of the following medications during screening, or in whom washout is medically inadvisable: anticonvulsants, mood stabilizers, anti-psychotic agents, opioids, benzodiazepines, non-benzodiazepine hypnotics (zolpidem, eszopiclone, zaleplon), buspirone, trazodone, stimulants (e.g., amphetamine mixed salts, methylphenidate, lisdexamphetamine, dextroamphetamine, modafanil, armodafanil), atomoxetine, or any medication known to be a potent (strong) cytochrome P450 subtype 3A4 (CYP3A4) inhibitor, or St. John's wort. **Note:** Use of caffeine and/or nicotine is permitted.
11. Unable to successfully wash out of alpha-adrenergic antagonists and/or agonists (e.g., prazosin, terazosin, doxazosin, tamsulosin, silodosin, tizanidine, clonidine, guanfacine) or when washout is medically inadvisable.
12. Positive results for illegal or abused substances other than cannabis at Screening or Baseline or history of alcohol/substance use disorder during the preceding 6 months as defined by the screening M.I.N.I. 7.0.2. Patients who utilize alcohol and/or cannabis but do not meet criteria for greater than MILD alcohol and/or substance use disorder are suitable for the study provided that, in the judgment of the Investigator, this usage will not interfere with the patient's ability to complete the study or provide reliable data.
13. Any clinically significant, uncontrolled, or unstable medical or surgical condition that could affect a patient's ability to participate in the study or potentially compromise a patient's well-being during the study, including patients with a history of untreated or uncontrolled angle-closure glaucoma.
14. Diagnosis of DSM-5-defined bipolar disorder I, II or unspecified, schizophrenia, schizoaffective disorder, obsessive-compulsive disorder, major depressive disorder (MDD) with psychotic features, other psychotic disorder, or antisocial personality disorder as confirmed by the M.I.N.I. Version 7.0.2.
15. History of or evidence for a diagnosis of borderline personality disorder (BPD) based on a score of \geq 7 on the McLean Screening Instrument (MLI) for BPD at Visit 1 (Screening) and Investigator determination that the rated symptoms of BPD are not simply due to overlap with PTSD symptomatology. Patients who score \geq 7 on the MLI may be

randomized upon Medical Monitor approval if the high score does appear to be a result of overlap of PTSD symptoms rather than presence of BPD.

16. Anticipated need for surgery that might confound results or interfere with patient's ability to comply with the protocol.
17. Female patients who are pregnant or lactating.
18. History of serotonin syndrome, severe allergic reaction or bronchospasm or known hypersensitivity to cyclobenzaprine or the excipients in TNX-102 SL or placebo formulations.
19. Seizure disorder other than history of childhood febrile seizures.
20. Current sleep apnea not well controlled by Continuous Positive Airway Pressure (CPAP) or oral (mouthpiece) devices. Patients with mild obstructive sleep apnea or those well controlled by CPAP or oral (mouthpiece) devices are allowed at the discretion of the Investigator.
21. Patients with a body mass index (BMI) > 40.
22. Has received any other investigational drug within 90 days before Screening or has taken cyclobenzaprine within 21 days before Randomization visit.
23. Previous participation in any other study with TNX-102 SL.
24. Any existing oral medical or dental condition, or tongue piercings, that could potentially interfere with sublingual administration of study drug, or history of severe or unexplained oral or oropharyngeal swelling or edema.
25. Family member of investigative staff.
26. In the process of litigating for compensation for a psychiatric disorder.

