6. Clinically significant laboratory abnormalities based on screening laboratory tests and/or medical history in the Investigator's opinion, including a Thyroid Stimulating Hormone (TSH) level > 1.5 times the upper limit of normal and aspartate aminotransferase (AST) and/or alanine aminotransferase (ALT) > 3 times the upper limit of normal (if persistent upon repeat). Patients with treated thyroid conditions and TSH levels ≤ 1.5 times the upper limit of normal will be eligible to participate in the study.
7. Diagnosed with clinically significant and currently relevant cardiac disease (e.g., significant arrhythmia; heart block; heart failure) or recent myocardial infarction [within the past 2 years] or QTcF > 450 msec (male) or > 470 msec (female) on the screening electrocardiogram (ECG).
8. Current evidence of human immunodeficiency virus (HIV) infection based on screening laboratory results or medical history, or clinically significant hepatitis B or C infection as defined by current treatment or liver function tests (e.g., aspartate aminotransferase [AST] or alanine aminotransferase [ALT] > 3 times the upper limits of normal).
9. Use of antidepressant medication within 2 months of Baseline, with the exception of trazodone at doses ≤ 150 mg per day or tricyclic antidepressants at doses ≤ 50 mg per day for the purpose of treating insomnia, which instead require a 1-week drug-free interval prior to the Baseline visit.

10. Unable to successfully wash out of the following medications during screening, or in whom washout is medically inadvisable: anticonvulsants, mood stabilizers, antipsychotic agents, opioids, benzodiazepines, non-benzodiazepine hypnotics (zolpidem, eszopiclone, zaleplon), buspirone, trazodone, stimulants (e.g., amphetamine mixed salts, methylphenidate, lisdexamphetamine, dextroamphetamine, modafinil, armodafinil), atomoxetine, or any medication known to be a potent (strong) cytochrome P450 subtype 3A4 (CYP3A4) inhibitor, or St. John's wort. **Note:** Use of caffeine and/or nicotine is permitted.
11. Unable to successfully wash out of alpha-adrenergic antagonists and/or agonists (e.g., prazosin, terazosin, doxazosin, tamsulosin, silodosin, tizanidine, clonidine, guanfacine) or when washout is medically inadvisable.

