8.4. Randomization Criteria

The following randomization criteria must be satisfied at the Visit 2 Baseline Randomization Visit in order for the patient to be eligible to continue in the study. Only those patients meeting all of the following randomization criteria are eligible for randomization:

1. Patient continues to meet all inclusion and exclusion criteria, including urine and blood test results, and
2. Visit 2 total CAPS-5 score ≥ 33 ("Symptom Severity version using 1-week recall), and
3. No active suicidal intent or plan, or suicidal behavior, based on Investigator's judgment and Visit 2 C-SSRS responses (e.g., no C-SSRS Type 4-5 ideation or suicidal behavior since Visit 1) and/or a score of > 4 on Item 10 of the Visit 2 MADRS.

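### Hyperthyroidism, a contraindication in the appended cyclobenzaprine label, is not a named exclusion, and the TSH rule has only an upper limit

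*Protocol*

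**What the plan says.** Exclusion 6 (Protocol 8.3, same rule in the synopsis) covers laboratory abnormalities that the investigator considers clinically significant, "including a Thyroid Stimulating Hormone (TSH) level > 1.5 times the upper limit of normal". It goes on to say that "Patients with treated thyroid conditions and TSH levels" no higher than "1.5 times the upper limit of normal will be eligible to participate in the study". No lower TSH limit is given.

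Two other places repeat the direction of the rule. Table 1, footnote c, makes TSH above the same limit exclusionary at Visit 1. Section 11.3.8 allows a repeat test and rules out patients whose values stay high.

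Section 10.1.4 and Table 1 call for free thyroxine whenever TSH lies outside the normal range on either side.

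The general safeguards are exclusion 13 ("Any clinically significant, uncontrolled, or unstable medical or surgical condition", where it could affect participation or well-being), the opening of 8.3 ("Eligible patients who meet any of the following criteria during the screening period should be excluded from the study"), the Visit 2 recheck in 8.4 ("Patient continues to meet all inclusion and exclusion criteria, including urine and blood test results") and medical monitor authorization before randomization (10.1.4).

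Appendix 3 reproduces the label of an extended-release oral cyclobenzaprine product. Hyperthyroidism appears there as a contraindication without qualification, in the highlights and in label section 4. The patient leaflet places it among the reasons not to take the drug.

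**The concern.** In hyperthyroidism TSH is typically suppressed, so an upper TSH limit cannot detect it. The one sentence that deals specifically with treated thyroid disease has no floor, and a patient who is treated but still hyperthyroid satisfies it. A site reading exclusion 6 alone could reasonably conclude that such a patient may enter.

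What is at stake is the safety of individual patients. The active ingredient is the same as in the label, dosing is daily for 12 weeks, and the schedule (Appendix 1) places both TSH and ECG at screening only. After randomization no further thyroid test or ECG is scheduled that would reveal a missed case; vital signs and adverse event review remain. The treatment comparison is not affected.

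**Working it through.** No arithmetic beyond counting applies. The check sets the label beside the protocol.

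**Step 1. Label contraindications (Appendix 3, label section 4) and their protocol counterparts**

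| Label group | Protocol counterpart |
|---|---|
| Hypersensitivity | Exclusion 18: "known hypersensitivity to cyclobenzaprine or the excipients in TNX-102 SL or placebo formulations" |
| MAO inhibitors | Section 15.3: such patients are not to be considered for the study |
| Cardiac disease | Exclusion 7: "Diagnosed with clinically significant and currently relevant cardiac disease (e.g., significant arrhythmia or heart block, heart failure) or recent myocardial infarction" |
| Hyperthyroidism | None by name |

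Three of the four groups have an explicit counterpart and one does not. None of the 26 exclusions, and none of the randomization criteria in 8.4, names hyperthyroidism.

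**Step 2. TSH eligibility statements**

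| Place | Rule | Lower limit |
|---|---|---|
| Synopsis, exclusion 6 | above 1.5 × ULN | none |
| 8.3, exclusion 6 | above 1.5 × ULN | none |
| Table 1, footnote c | above 1.5 × ULN | none |
| 11.3.8 | still high on repeat | none |

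All four address high TSH only. They amount to one rule stated several times, so the count shows consistency and not four separate gaps.

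**Step 3. Use of free thyroxine.** The test is triggered by low as well as high TSH (10.1.4, Table 1). The plan therefore anticipates a low TSH and collects the result needed to interpret it. No visible eligibility rule refers to that result.

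**Step 4. A test case.** Take a treated patient with TSH below normal and raised free thyroxine.

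- Numeric part of exclusion 6: not met, because TSH is not above 1.5 × ULN.
- Treated-thyroid sentence of exclusion 6: satisfied, which points to eligibility.
- Leading clause of exclusion 6: met if the investigator calls the abnormality clinically significant.
- Exclusion 13: met if the condition is judged clinically significant, uncontrolled or unstable, and able to affect participation or well-being.
- Medical monitor: may refuse authorization, but no thyroid criterion is visible.

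Every route to exclusion passes through judgment, and the specific text points the other way.

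**Step 5. Comparison within exclusion 13.** That item names untreated or uncontrolled angle-closure glaucoma, for which label section 5.5 advises only caution. A label precaution is thus named while a label contraindication is not.

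**The case against.** The strongest reply is that the protocol, read as a whole, already excludes this patient. The TSH limit in exclusion 6 is an example under a broader clause. The treated-thyroid sentence clarifies that limit and does not waive exclusion 13. Meeting any one exclusion is enough, and the criteria are rechecked at Visit 2. Screening includes history, vital signs, ECG, a physical examination that covers the neck, and free thyroxine when TSH is low; a medical monitor must then agree. This stands as far as it goes: a careful site would probably exclude overt disease. It does not remove the conflict between a permissive specific sentence and a discretionary general clause.

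Second, the label is not stated to be this trial's entry standard. It covers 15 and 30 mg oral extended-release capsules, whereas the trial gives 5.6 mg sublingually. The protocol departs from the label on duration (12 weeks against 2 to 3) and on age (up to 75, although use in the elderly is not recommended). So a mismatch is not by itself a defect. However, the protocol does refer to Appendix 3 for safety information on the active ingredient (12.4), and the visible text gives no reason for leaving this contraindication out.

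Third, the other counterparts are imperfect too. The cardiac exclusion is qualified by clinical significance, and the MAO inhibitor rule sits in the consent section. That is fair: reliance on judgment is common in this protocol. Those two conditions are nevertheless named.

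Fourth, a thyroid rule may exist in the blacked-out section 5.1.1, the Investigator's Brochure or the separate document on pre-randomization review. This cannot be checked and limits how firmly the point can be put.

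**Conclusion.** The point holds as a minor, optional improvement to patient-safety wording. Hyperthyroidism is the one label contraindication group of four without a named counterpart, no TSH statement has a lower limit, and no visible eligibility rule uses free thyroxine. The general clauses and the monitor's review reduce the risk without settling the matter.

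The frequency of affected patients cannot be derived from the documents, and no effect on the efficacy estimate is claimed. The conclusion assumes that the contraindication carries over by active ingredient despite the different dose and route, and that no thyroid rule sits in the material not available. Low TSH alone is not the labelled contraindication. Confidence is medium.

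**What to change.** Add to exclusion 6, in the synopsis and in 8.3: *current hyperthyroidism (for example, TSH below the lower limit of normal with raised free T4)*. Limit the treated-thyroid sentence to patients who are not currently hyperthyroid and whose TSH is at or below 1.5 × ULN. Align 11.3.8 and Table 1, footnote c, and state there how the reflex free T4 result decides eligibility. Leave low TSH with normal free T4 to the investigator and the medical monitor.

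This changes wording in four places and adds no test, because screening TSH and reflex free T4 already supply the data. It is a protocol modification, so section 14.1 requires EC/IRB approval before use. The other cost is possibly a few more screen failures.

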8.4. Randomization Criteria

The following randomization criteria must be satisfied at the Visit 2 Baseline Randomization Visit in order for the patient to be eligible to continue in the study. Only those patients meeting all of the following randomization criteria are eligible for randomization:

1. Patient continues to meet all inclusion and exclusion criteria, including urine and blood test results, and
2. Visit 2 total CAPS-5 score ≥ 33 ("Symptom Severity version using 1-week recall), and
3. No active suicidal intent or plan, or suicidal behavior, based on Investigator's judgment and Visit 2 C-SSRS responses (e.g., no C-SSRS Type 4-5 ideation or suicidal behavior since Visit 1) and/or a score of > 4 on Item 10 of the Visit 2 MADRS.

8.5. Prior and Concomitant Medications

Many concomitant psychiatric medications are prohibited during this study because this study has been designed to evaluate the safety and efficacy of monotherapy with TNX-102 SL tablets

for the treatment of PTSD. The goal of the study is to recruit patients who are not currently using other medications to treat their PTSD, or who are not clearly benefitting from any of the medications that would need to be discontinued in order to enter this study. Since many patients with PTSD may already be taking one or more excluded medications when screened, Principal Investigators should use extreme caution when determining whether a patient, in their clinical judgment, can be safely withdrawn from current medications that are being used to treat PTSD or are otherwise excluded from the protocol.

Eligible patients will not be receiving treatment with antidepressants, antipsychotic agents, mood stabilizers or anticonvulsants. In addition, eligible patients will not have taken antidepressants within 2 months of the Baseline visit. This time frame is intentionally long because it is not considered appropriate for patients to discontinue antidepressants solely to enter the study. An exception is made for the use of low-dose tricyclic agents at doses \leq 50 mg per day, or trazodone at doses \leq 150 mg per day for the purpose of treating insomnia, either of which may be discontinued for the purpose of enrollment but requires a 1-week medication-free period prior to randomization, as described below.

Patients also must be willing and able to discontinue use of benzodiazepines, non-benzodiazepines and certain other medications frequently used to treat PTSD; e.g., prazosin; trazodone; topiramate. Discontinuation of any of these agents should only be considered if/when the patient's clinical condition and stability will not be adversely affected.

Unless otherwise stated, excluded medications (e.g., trazodone, prazosin, topiramate, alpha-adrenergic agonists or antagonists [e.g., prazosin; tamsulosin; terazosin; doxazosin, silodosin, alfuzosin, clonidine, guanfacine], buspirone, benzodiazepines, and non-benzodiazepine hypnotics [zolpidem, zaleplon, eszopiclone]) will require a 1-week drug-free period prior to the Baseline visit (Visit 2). Several benzodiazepines are not easily detected by the in-clinic urine dipstick; therefore, any patient whose screening UDS is positive for benzodiazepines should undergo repeat urine testing after washout, and that sample should be sent to the central laboratory for centralized interpretation. Because of this, the Baseline visit may need to be delayed to provide sufficient time for the results of the repeat, post-washout drug screen to be returned to the site, since the patient should not be randomized until negative results have been confirmed. It is recommended that the Baseline visit is scheduled no sooner than 7 days after the patient's post-washout urine drug screen, to ensure the results are available for review at the Baseline visit.

Similarly, all opioid medications, including tramadol and tapentadol, are excluded medications. Patients on chronic opioids are not appropriate candidates for participation, but there may be patients with occasional PRN opioid usage or who were recently on a short course for acute pain who may be appropriate if, in the clinical judgement of the Investigator, they could be safely tapered and remain opioid free for the week before baseline visit and throughout the 12 weeks of the study. The screening period of up to 21 days is provided to ensure a safe tapering rate and discontinuation of excluded medications, per Investigator's discretion, leading up to the 1-week medication-free period required before the randomization/baseline visit.

Other medications capable of modifying the pharmacologic activity of TNX-102 SL (e.g., α -adrenergic agonists/antagonists; potent CYP3A4 inhibitors) will also be excluded, and discontinuing these medications should only be considered if clinically acceptable. A list of

CYP3A4 inhibitors is provided in [Appendix 2](#); only those considered potent or strong inhibitors (in the left-hand column) are excluded medications.

8.5.1. Allowed Concomitant Medications

It is ideal to have all patients participating in the study go without any hypnotic agents for the entire double-blind period of the study. Yet there may be instances in which patients' insomnia symptoms need to be addressed with a concomitant treatment. In these instances, the Investigator should recommend use of an antihistamine-based OTC hypnotic, such as Benadryl® or generic diphenhydramine 25-50 mg, for a limited period (e.g. no more than a few nights in a row). Patients should be asked to keep track of their use of such sleeping remedies, and again, chronic nightly use should be avoided whenever possible.

Melatonin is considered an allowable concomitant medication but its usage should have been stable for at least 30 days prior to baseline and usage should remain stable during the study. If diphenhydramine is ineffective, the treating Investigator should contact the medical monitor to discuss alternative options.

Allergy medications and cold remedies containing adrenergic agonist decongestants such as pseudoephedrine or phenylephrine should be avoided unless absolutely necessary (and in such cases when considered absolutely necessary, they should be avoided in the evening or at bedtime to minimize their interference with sleep). Sympathomimetics such as adrenergic agonist decongestants have the potential to acutely worsen PTSD symptoms and therefore could confound the assessment of TNX-102 SL versus placebo for treatment of PTSD.

Other prescription or over-the-counter medications not specifically excluded by entry criteria typically may be continued during the study, with the expectation that chronic medications should have been used in a stable fashion for at least 30 days prior to randomization. Sites should contact the medical monitor for any questions about whether a concomitant medication may be continued during the study or if it would be acceptable to taper an excluded medication.

